### 10.6.2 Prior and concomitant therapy

In general, no concomitant medications or therapies, including herbal remedies, vitamin supplements and over-the-counter (OTC) products, will be allowed during participation in the study.

In particular, intake of medications which could influence folate and vitamin B12 status is prohibited during the study.

However, the following will be allowed:

- Paracetamol in doses up to 2000 mg/day for a maximum of 3 consecutive days. If this amount of paracetamol is not sufficient for treatment of the subject, withdrawal should be considered.
- Nasal decongestants without cortisone or antihistamine for a maximum of 10 days.

Other medications considered necessary for the subject's safety and well-being, may be given at the discretion of the Investigator during the residential period. Following consultation with the Sponsor, the Investigator will determine whether or not the subject should continue in the study.

## 10.7 Criteria for subject withdrawal

### 10.7.1 General withdrawal criteria

Subjects are free to discontinue their participation in the study at any time and for whatever reason without affecting their right to an appropriate follow-up investigation or their future care. If possible, the reason for withdrawal of consent should be documented.

Subjects may be discontinued from the study at any time at the discretion of the Investigator for any of the following reasons:

- Severe non-compliance to study protocol procedures, as judged by the Investigator and/or Sponsor.
- Subject is lost to follow-up.
- Significant AEs posing a risk for the subject, as judged by the Investigator and/or Sponsor.
- Withdrawal of informed consent to the use of biological samples.

#### 10.7.1.1 QTc withdrawal criteria

A subject meeting the criteria below will be withdrawn from the study. The same QT correction formula will be used to determine discontinuation throughout the study.

- QTcF > 500 millisecond (msec)
- Change from baseline: QTc > 60 msec to QTc > 480 msec

Withdrawal decisions will be based on an average QTc value of triplicate ECGs. If an ECG demonstrated a prolonged QT interval, two more ECGs will be obtained over a brief period and the averaged QTc values of the three ECGs used to determine whether the subject should be discontinued from the study.

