#### **Duration of treatment**

Each subject will receive a single bolus *i.v.* injection of IMP or Placebo on study Day 1.

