##### 10.7.1 Subject replacement

Subjects who are prematurely withdrawn from the study for any reason except the occurrence of Treatment-emergent AEs (TEAEs) assessed as possibly or probably related to study treatment may be replaced during the course of the study.

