## 11.6 Treatment administration

The pre-defined dose levels are 200, 350 and 500 mg/m^2 of Modufolin® for Injection, 100 mg. There will be 3 cohorts, 11 subjects in each cohort. Subjects will be assigned to a cohort in a consecutive manner. In each cohort, 8 subjects will receive Modufolin® for Injection, 100 mg and 3 subjects will receive placebo. The IMP/placebo will be administered as a single dose on Study Day 1. The IMP/placebo will be administered in the morning and the time will be recorded in the CRF. The study subjects should be fasting overnight (8 hrs) before IMP/placebo administration until 4 hrs post-dose. There will be an interval of at least 7 days between each cohort to allow time for the iSRC to evaluate safety data before proceeding to the next dose level.

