### Route of administration

Intravenous bolus injection (injection time 3 min).

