#### 17.3.2 Per Protocol Analysis Set

The Per Protocol Analysis Set will consist of all subjects who have been randomized and completed the study period without any major protocol deviations. All protocol violations will be judged as major or minor at the clean file meeting.

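### The QTc criterion ends study participation in a single-dose trial, so as written it stops serial ECG/PK collection in the largest QTc responders while no dosing remains to stop

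*Protocol*

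**What the plan says.** **Dosing.** Section 11.6: "The IMP/placebo will be administered as a single dose on Study Day 1". The injection lasts 3 minutes.

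**QTc criterion.** Section 10.7.1.1: "A subject meeting the criteria below will be withdrawn from the study". The triggers are a QTcF above 500 msec, or "Change from baseline: QTc > 60 msec to QTc > 480 msec", judged on the average of three ECGs.

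**After discontinuation.** Section 10.7.2 provides an investigator assessment along the lines of the follow-up visit, where possible, and follow-up of ongoing adverse events. It does not mention the remaining Holter extractions or PK samples of Table 1. Section 17.6.2 describes telemetry to 24 h without saying whether it covers withdrawn subjects.

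**Replacement.** The section headed Subject replacement (a second section numbered 10.7.1) says that withdrawn subjects "may be replaced during the course of the study", except where the reason is a treatment-emergent adverse event (TEAE) judged possibly or probably related.

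**Analysis sets.** The QT/QTc set (17.3.5) needs one valid post-dose ΔQTcF value; the PK/QTc set (17.3.6) needs one post-dose PK/QTcF pair. The PK analysis (17.7.5) uses the Per Protocol Analysis Set, whose members "completed the study period without any major protocol deviations" (17.3.2).

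**The concern.** A withdrawal criterion of this kind normally protects a subject from further dosing. Here a post-dose ECG can meet it only after the whole dose has been given. What it ends is participation, and with it, read literally, the serial collection that the trial is built on.

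The loss is informative because the trigger measures the same quantity as the primary endpoint, change-from-baseline QTcF. Time points go missing because the QTc response was large. An analysis plan can describe how missing values are handled, but it cannot recover recordings and samples that the protocol stopped collecting.

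The later times matter. Section 17.4.3 plans hysteresis plots if 10 msec cannot be excluded by time point in the two highest dose groups, and these need the full time course. Appendix 18.3 gives a time to peak of 3 to 6 h for the methyl-THF metabolite at 200 mg/m², so an effect that followed this metabolite would fall in the window that could be lost.

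**Working it through.** **1. The plan's own power figure.** Inputs from section 17.2: SD 7 msec, true effect 3 msec, limit 10 msec, one-sided 0.05, 24 active and 9 placebo.

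- SE = 7 × √(1/24 + 1/9) = 2.736
- z = (10 − 3)/2.736 − 1.645 = 0.914, so power = 82.0%
- For 48 and 18: SE = 1.935, z = 1.973, power = 97.6%

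Both stated figures (82% and 97.5%) reproduce. Losing one or two active subjects without replacement gives 81.6% or 81.1%. Power is not the issue.

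**2. How often the rule would act under the planning assumptions.**

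- P(change > 60) = P(Z > (60 − 3)/7) = P(Z > 8.14), about 2 × 10⁻¹⁶.
- The absolute limit of 500 can be reached by a smaller change. With baseline no higher than the screening cap of 450 (exclusion criterion 6; assumed still to hold on Day 1), a change above 50 is needed: P(Z > (50 − 3)/7) = P(Z > 6.71), about 10⁻¹¹.

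So the rule has essentially no effect if the drug behaves as planned.

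**3. How often it would act if the drug does prolong QTc.** The protocol gives no figures for this case. Assuming a mean change of 20 to 30 msec with SD 15:

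- Mean 20: P(Z > (60 − 20)/15) = P(Z > 2.67) = 0.4%
- Mean 30: P(Z > (60 − 30)/15) = P(Z > 2.00) = 2.3%

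These are per subject at the peak, and they are ceilings for the change-based trigger, which also needs QTc above 480. A subject whose baseline is below 480 − 60 = 420 must change by more than 60.

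**4. What is lost when it acts.** The post-dose times in Table 1 are 5, 15 and 30 min and 1, 2, 3, 4, 5, 6, 8, 12 and 24 h: 12 in all. Section 9.2 says post-dose ECG extractions are paired with PK samples. If the criterion is met at 1 h (an assumption; the safety-ECG times cannot be read reliably from the extracted table), the 8 times from 2 to 24 h are lost. One subject is 1/8 = 12.5% of a dose group.

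**5. What is kept, by analysis.**

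| Analysis | Set | Subject withdrawn under 10.7.1.1 |
|---|---|---|
| By time point, categorical | QT/QTc | Kept up to withdrawal; later times missing |
| Exposure-response (primary) | PK/QTc | Kept up to withdrawal; later pairs missing |
| PK parameters | Per protocol | Excluded, because he did not complete |

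The primary prediction in 17.4.3 is made at the geometric mean of individual Cmax values. The protocol does not say from which set these come. If they come from the per-protocol PK analysis, his exposure drops out there too.

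**6. Replacement.** A clinically significant abnormal ECG can be an adverse event (12.5.1.1). If it is recorded as one and judged possibly or probably related, replacement is barred. If it is not recorded as an event, or is judged unrelated, replacement is open. Section 10.7.1.1 does not settle which applies.

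**The case against.** A reader might infer that the rule deletes high QTc values and can turn a positive finding into a false conclusion of no effect. In a worst case, let one of 24 active subjects have a change of 65 msec (assumed) and the others average 3. With him kept, the mean is (23 × 3 + 65)/24 = 5.6 and the expected upper bound about 14.1 msec. With him wholly absent and replaced by an ordinary subject, these become 3.0 and 7.6, across the 10 msec limit. The documents do not support this reading: sections 17.3.5 and 17.3.6 keep every value up to withdrawal, including a Holter value at the triggering time, and the categorical analysis would still count it.

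Other parts of the opposing case also stand:

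- After a bolus, peak parent concentration comes at the earliest samples. Appendix 18.3 reports a terminal half-life of 1.5 to 1.8 h at 200 mg/m² (two patients), with most of the exposure gone sooner. The pairs at risk are mainly at low concentration.
- The decision rests on averaged triplicate ECGs, apparently the on-site safety ECGs of 12.4.1. The endpoint comes from centrally read Holter extractions. The two are closely related but not the same data.
- Replacement is optional, and a marked prolongation soon after dosing may well be judged possibly related, which bars it.
- A reader might also infer that safety monitoring stops. Sections 10.7.2, 12.5.6 and 17.6.2 keep an assessment, adverse-event follow-up and telemetry in view, and nothing orders discharge. The text is silent on the point rather than contradictory.

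None of this answers the central point: the stated consequence is withdrawal from the study, and no section says that serial collection continues.

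**Conclusion.** The point holds in limited form. Followed as written, section 10.7.1.1 stops no treatment and cuts short ECG/PK collection selectively in the largest QTc responders. The bias concerns later time points, any delayed effect and the PK summary, and replacement of such a subject remains possible.

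Its size depends on a response the planning assumptions do not foresee. At mean 3 and SD 7 msec the chance of triggering is practically nil. At an assumed mean of 20 to 30 and SD 15, at most about 0.4 to 2.3% of subjects would meet the change-based trigger at peak. One such subject, if withdrawn at 1 h, loses 8 of 12 pairs in a group of 8. It is still worth correcting, because the rule acts only when a large effect occurs, which is what the trial is meant to characterise, and the correction needs wording only.

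**What to change.** Reconcile sections 10.7.1.1, 10.7.2, Subject replacement, 17.3.2, 17.6.2 and 17.7.5 with the single-dose design, separating the clinical decision from data collection. Thresholds and care stay with the sponsor and the investigator; no change to them is proposed. The text should state that:

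1. meeting the QTc criterion does not by itself end the already scheduled ECG, PK and safety data collection to 24 h and follow-up, subject to consent and the investigator's clinical judgement;
2. the subject's data are kept in the ECG analyses and in the PK analysis, whatever his completion status for the per-protocol set;
3. any subject added afterwards supplements him and does not substitute for him.

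The cost is protocol wording. The assessments are already in the schedule, so no visit or procedure is added.

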#### 10.7.1.2 Liver chemistry withdrawal criteria

Liver chemistry threshold stopping criteria have been designed to assure subject safety and to evaluate liver event etiology.

Study treatment will be stopped if any of the following liver chemistry stopping criteria is met:

- Alanine transaminase (ALT) 3 x Upper Limit of Normal (ULN) and total bilirubin  $\geq$  2xULN ( $>35\%$  direct bilirubin); **or** ALT 3xULN and INR  $> 1.5$

*NOTE: serum bilirubin fractionation should be performed if testing is available. If fractionation is unavailable, urinary bilirubin is to be measured via dipstick (a measurement of direct bilirubin, which would suggest liver injury).*

- ALT 5xULN.
- ALT 3xULN if associated with symptoms (new or worsening) believed to be related to hepatitis (such as fatigue, nausea, vomiting, right upper quadrant pain or tenderness or jaundice) or believed to be related to hypersensitivity (such as fever, rash or eosinophilia).

Subjects with ALT 3xULN **and**  $< 5xULN$  **and** bilirubin  $< 2xULN$ , who do not exhibit hepatitis symptoms or rash, will be allowed to continue study treatment as long as they are monitored weekly for four weeks.

#### 10.7.2 Procedures for discontinuation of a subject from the study

A subject who prematurely discontinues participation in the study will always be asked about the reason(s) for discontinuation and the presence of any AEs. If possible, they will be seen by the Investigator and assessed according to the procedures scheduled for the follow-up visit. Any ongoing AEs will be followed as described in Section 12.5.6.

##### 10.7.1 Subject replacement

Subjects who are prematurely withdrawn from the study for any reason except the occurrence of Treatment-emergent AEs (TEAEs) assessed as possibly or probably related to study treatment may be replaced during the course of the study.

### 10.8 Randomisation

Subjects in each cohort will be randomized to receive either placebo (3 subjects) or active treatment (8 subjects).

The randomization list will be generated by CTC or delegate and provided to the packing company. The original randomization list will be kept in a sealed envelope by the randomizer. Sealed treatment code envelopes will be kept by CTC and the Sponsor.

## 10.9 Blinding

This is a double-blinded study and the allocation of treatments will not be disclosed until clean file has been declared and the database has been locked.

The IMP and the placebo are not identical in appearance and all efforts will be made at the clinic in order to maintain the blind. Both the IMP and the placebo will be masked in such a way that study subjects and study staff will remain blinded during the study. An un-blinded study nurse will prepare the IMP/placebo and administer the solutions to the study subject. The un-blinded study nurse will not be involved in any study-specific assessments or evaluations.

## 10.10 Emergency decoding of blinded treatment during the study

The treatment code may only be broken by the study medical staff in case of emergency when knowledge of the treatment received is necessary for the proper medical management of the subject. The code breaking procedure should be carefully documented in the CRF.

The randomization code may be broken by the iSRC during the assessment process (partial un-blinding) but only for subjects with severe AEs ( $\geq$ grade 3) to enable their decision on continued dosing of further cohorts or to stop the dose escalation. The medical staff and the subjects will still be blinded for the treatments (active drug or placebo) to be administered in the subsequent cohorts in order to minimize bias (see Section 9.2).

# 11 TREATMENTS

## 11.1 Identity of Investigational Medicinal Product

Test product (Modufolin® for Injection, 100 mg)

### Pharmaceutical formulation

Modufolin® for Injection, 100 mg is formulated as a lyophilized white to light yellowish or light beige powder containing 100 mg Modufolin® per vial (calculated as free acid, for composition see Table 3). After reconstitution with 10 mL sterile water, reconstituted Modufolin® Injection, 100 mg is a clear yellowish fluid ready for intravenous (*i.v.*) use as bolus injection (final concentration of 10 mg/mL). The resulting solution for injection is isotonic and has a pH of 8.5.

**Table 3 Composition of pharmaceutical formulation**

Component	Amount/vial	Function
Sodium hydroxide	0.3 g	For pH adjustment
Trisodium citrate dihydrate	0.2 g	Buffer (to guarantee a defined stable pH after reconstitution in water)
Modufolin ® drug substance	0.1 g	Active pharmaceutical ingredient

## 11.2 Non- Investigational Medicinal Product (Placebo)

The placebo in this study will be 0.9% NaCl sterile solution.

## 11.3 Packaging and labelling of Investigational Medicinal Product

The drug product, Modufolin® for Injection, 100 mg is manufactured, released and tested in compliance with Good Manufacturing Practice (GMP) by the following companies as summarised in Table 4.

**Table 4 Manufacturers of IMP**

Name	Address	Function
Cobra Biopharma Matfors AB (previously Unitech Biopharma AB)	[name] [name], Sweden	Manufacture Batch release
Merck & Cie	[name] [name] Switzerland	Release testing
Unimedic AB	[name] [name], Sweden	Release testing (particulate matter)
Pharmacontrol MQL AB	[name] [name] Sweden	Release testing (sterility)

Primary packaging (Modufolin® for Injection, 100 mg):

Lyophilized powder: 10 mL type 1 glass vials with lyophilization stopper (20 mm, siliconized, Helvoet FM157).

Secondary packaging (Modufolin® for Injection, 100 mg):

Each box will contain 10 x 10 mL glass vials.

Labels will comply with applicable current Good Manufacturing Practice (GMP) requirements.

The following labels will be used for Study ISO-FF-001:

*Primary packaging- Label to be attached to vial*

For clinical trial	Study No. ISO-FF-001
Caution: New Drug--Limited by Federal law to investigational use	
Modufolin® for Injection, 100 mg	
Batch No: XXXX	
Store at 2 - 8°C (refrigerator)	
Principal investigator: [name]	
Sponsor: Isofol Medical AB, [contact]	

*Secondary packaging- Label to be attached to each box containing 10 vials*

For clinical trial	Study No. ISO-FF-001
Principal investigator: [name]	
Caution: New Drug--Limited by Federal law to investigational use	
Modufolin® for Injection, 100 mg	
10x100mg	
To be dissolved with Water for Injection according to separate preparation description	
Batch No: XXXX	Expiry date: YYYY-MM-DD
Store at 2 - 8°C (refrigerator)	
Sponsor: Isofol Medical AB, [name] [name] [contact]	

#### 11.4 Conditions for storage

Modufolin® for Injection, 100 mg vials are stored at refrigerated storage conditions 2-8 °C. Stability data demonstrate that the drug product is stable when stored at 2-8 °C for up to 48 months. The current shelf life is 42 months.

Stability data on the solution for injection (the dissolved powder) show that the reconstituted IMP is stable for up to 2 hrs at room temperature after reconstitution.

## 11.5 Dispensing and accountability

CTC AB and the Investigator will maintain a *Drug Dispensing Log* detailing the dates and quantities of study medication received, dispensed to and used by each subject and study medication returned or destroyed at the end of the study. Any discrepancies between dispensed and returned IMP must be explained and documented. Products deliberately and/or accidentally destroyed by the Investigator/ pharmacy or the subject must be accounted for.

## 11.6 Treatment administration

The pre-defined dose levels are 200, 350 and 500 mg/m^2 of Modufolin® for Injection, 100 mg. There will be 3 cohorts, 11 subjects in each cohort. Subjects will be assigned to a cohort in a consecutive manner. In each cohort, 8 subjects will receive Modufolin® for Injection, 100 mg and 3 subjects will receive placebo. The IMP/placebo will be administered as a single dose on Study Day 1. The IMP/placebo will be administered in the morning and the time will be recorded in the CRF. The study subjects should be fasting overnight (8 hrs) before IMP/placebo administration until 4 hrs post-dose. There will be an interval of at least 7 days between each cohort to allow time for the iSRC to evaluate safety data before proceeding to the next dose level.

### Route of administration

Intravenous bolus injection (injection time 3 min).

### Preparation and handling of IMP solution (Modufolin® for Injection, 100 mg):

1. The preparation of the solution for injection will be done by trained personnel, for example a site pharmacist or a registered nurse. There will be 2 un-blinded persons working together, one person will handle the IMP and perform the reconstitution of the drug product while the other person will supervise the process. The process will also be recorded on video tape.
2. The reconstitution of each vial of IMP powder in 10 mL of water for injection should be done using aseptic technique.
3. Gently swirl each vial until the powder is completely dissolved. The resulting solution is clear and ranges in color from colorless to yellow.
4. The solution should be inspected visually for particulate matter and discoloration prior to administration. If particles are present, do not administer.
5. The reconstituted solution can be kept at room temperature.
6. Administration should preferably be done directly after reconstitution and must be done within 2 hrs after reconstitution.
7. If administration cannot take place for whatever reason, the vial should be handled in accordance with the study-specific instructions on IMP disposal.

## 11.7 Continuation of treatment with Investigational Medicinal Product

This is a Phase I study in healthy volunteers who will have no medical benefit from the treatment and thus there will be no treatment with Modufolin® for Injection, 100 mg after end of study participation.

## 11.8 Treatment compliance

All study products will be administered at the research clinic under medical supervision to ensure compliance.

## 11.9 Return and destruction of Investigational Medicinal Product

Any unused IMP will be returned to the Sponsor or the Hospital Pharmacy for destruction. Empty containers will be destroyed at the study site. The Monitor will perform final IMP accountability reconciliation at the study end to verify that all unused IMP is adequately destroyed/returned and documented.

# 12 STUDY ASSESSMENTS

The study assessments are described in the sections below and the timing of these assessments are detailed in the Schedule of events in Section 9.1 (Table 1).

## 12.1 Recording of data

The Principal Investigator will provide the Sponsor with all data produced during the study from the scheduled study assessments. He/she ensures the accuracy, completeness, legibility, and timeliness of the data reported to Sponsor in the CRF and in all required reports.

When time points for ECG recordings coincide with other assessments, procedures should be carried out in the following order:

1. Holter ECG
2. Safety ECG
3. Vital sign
4. PK blood sampling
5. Safety blood sampling.

The actual PK blood sampling time should always be recorded in the CRF and will be used in the calculation of the PK parameters. Pre-dose assessments may be performed up to 60 min prior to dosing if not specified in the Schedule of events in Section 9.1 (Table 1).

## 12.2 Demographics and other baseline characteristics

### 12.2.1 Informed consent

Signed informed consent must be obtained before any screening procedures are initiated. The informed consent procedure is further described in Section 14.3.

